6.1.4 Monitoring of RAD001 Suspected Toxicities

Patients whose treatment is interrupted or permanently discontinued due to an AE or abnormal laboratory value suspected to be related to RAD001 must be followed at least weekly until the AE or abnormal laboratory value resolves or returns to grade 1.

If a patient requires a dose delay of >21 days from the intended day of the next scheduled dose, then the patient must be discontinued from the study.

6.1.4.1 Management of Stomatitis/Oral Mucositis/Mouth Ulcers

Stomatitis/oral mucositis/mouth ulcers due to RAD001 should be treated using local supportive care. Please note that investigators in earlier studies have described the oral toxicities associated with RAD001 as mouth ulcers, rather than mucositis or stomatitis.

If examination reveals mouth ulcers rather than a more general inflammation of the mouth, the AE should be classified as such. Please follow the paradigm below for the treatment of stomatitis/oral mucositis/mouth ulcers:

1. For mild toxicity (grade 1), conservative measures such as non-alcoholic mouth wash or salt water (0.9%) mouth wash several times a day until resolution should be used.
2. For more severe toxicity (grade 2, in which case patients have pain, but are able to maintain adequate oral alimentation, or grade 3, in which case patients cannot maintain adequate oral alimentation), the suggested treatments are topical analgesic mouth treatments (i.e., local anesthetics such as benzocaine, butyl aminobenzoate, tetracaine hydrochloride, menthol, or phenol) with or without topical corticosteroids, such as triamcinolone oral paste 0.1% (Kenalog in Orabase[®]).
3. Agents containing hydrogen peroxide, iodine, and thyme derivatives may tend to worsen mouth ulcers. It is preferable to avoid these agents.
4. Antifungal agents must be avoided unless a fungal infection is diagnosed. In particular, systemic imidazole antifungal agents (ketoconazole, fluconazole, itraconazole, etc.) should be avoided in all patients due to their strong inhibition of RAD001 metabolism, leading to higher RAD001 exposures. Therefore, topical antifungal agents are preferred if an infection is diagnosed. Similarly, antiviral agents such as acyclovir should be avoided unless a viral infection is diagnosed.

Note: Stomatitis/oral mucositis should be appropriately graded using the functional grading given on the National Cancer Institute- (NCI) CTC for Adverse Events (CTCAE), version 3.0.

6.1.4.2 Management of Hyperlipidemia and Hyperglycemia

Treatment of hyperlipidemia should take into account the pre-treatment status and dietary habits of the patient. Blood tests to monitor hyperlipidemia must be taken in the fasting state.

Grade 2 or higher hypercholesterolemia (>300 mg/dL or 7.75 mmol/L) or grade 2 or higher hypertriglyceridemia ($>2.5 \times$ ULN) should be treated with a statin or appropriate lipid-lowering medication, in addition to diet. Patients should be monitored clinically and through

serum biochemistry for the development of rhabdomyolysis and other AEs as required in the product label/data sheets for HMG-CoA reductase inhibitors.

Note: Concomitant therapy with fibrates and an HMG-CoA reductase inhibitor is associated with an increased risk of a rare, but serious, skeletal muscle toxicity manifested by rhabdomyolysis, markedly elevated creatine phosphokinase levels and myoglobinuria, acute renal failure, and sometimes death. The risk versus benefit of using this therapy should be determined for individual patients based on their risk of cardiovascular complications of hyperlipidemia.

Grade 3 hyperglycemia has been observed in patients receiving RAD001 therapy. In many cases in Study RAD001C2222, the affected patients had an abnormal fasting glucose at baseline. Based on this finding, it is recommended that optimal glucose control be achieved before starting a patient on RAD001. Study patients should have their glucose levels monitored during RAD001 therapy.

6.1.4.3 Management of Non-Infectious Pneumonitis

Both asymptomatic radiological changes (grade 1) and symptomatic non-infectious pneumonitis (grade 2 = not interfering with activities of daily living or grade 3 = interfering with activities of daily living and oxygen indicated) have been noted in patients receiving RAD001 therapy. Non-infectious pneumonitis has been associated with RAD001 and other mTOR inhibitors (Atkins, et al., 2004).

In order to monitor for asymptomatic (grade 1) non-infectious pneumonitis, a chest x-ray or CT scan is required in addition to the 3-monthly CT or magnetic resonance imaging (MRI) tumor examinations.

Additional chest x-rays or CT scans may be performed, when clinically necessary. If non-infectious pneumonitis develops, a consultation with a pulmonologist should be considered. If the patient develops grade 3 pneumonitis, treatment with RAD001 should be interrupted and the patient should be treated as medically indicated (short course corticosteroids, oxygen, etc.).

Chest x-ray/chest CT scans obtained during the study should be readily accessible at the site and must be kept with the patient's source documents.

Dose modification instructions and Management of non-infectious pneumonitis suspected to be associated with RAD001 and are provided in [Table 3](#) and [Table 4](#).

Table 4 Management of Non-Infectious Pneumonitis

Worst Grade Pneumonitis	Required Investigations	Management of Pneumonitis	RAD001 Dose Adjustment
Grade 1	CT scans with lung windows. Repeat every 3 cycles until return to within normal limits.	No specific therapy is required.	Administer 100% of RAD001 dose.
Grade 2	CT scans with lung windows and required pulmonary function testing includes: spirometry, DLCO, and room air O ₂ saturation at rest. Repeat each subsequent cycle until return to baseline. Consider a bronchoscopy. ^a	Symptomatic only. Prescribe corticosteroids if cough is troublesome.	Reduce RAD001 dose until recovery to ≤ grade 1. RAD001 may also be interrupted if symptoms are troublesome. Patients should be withdrawn from the study if they fail to recover to ≤ grade 1 within 3 weeks.
Grade 3	CT scans with lung windows and required pulmonary function testing includes: spirometry, DLCO, and room air O ₂ saturation at rest. Repeat each subsequent cycle until return to baseline. Bronchoscopy ^a is required.	Prescribe corticosteroids if infective origin is ruled out. Taper as medically indicated.	Hold treatment until recovery to ≤ grade 1. May restart protocol treatment within 2 weeks at a reduced dose (by one level) if evidence of clinical benefit.
Grade 4	CT scans with lung windows and required pulmonary function testing includes: spirometry, DLCO, and room air O ₂ saturation at rest. Repeat each subsequent cycle until return to baseline. Bronchoscopy ^a is required.	Prescribe corticosteroids if infective origin is ruled out. Taper as medically indicated.	Discontinue treatment.

^a A bronchoscopy with a biopsy and/or bronchoalveolar lavage is required.
Abbreviations: CT = computerized tomography; DLCO = diffusion capacity of carbon monoxide.

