6.1.3 RAD001 Dose Level Modification/Interruption Guidelines in Case of Suspected Toxicity

Dose adjustments are permitted in those patients who are unable to tolerate the protocol-specified dosing schedule. If administration of RAD001 must be interrupted because of unacceptable toxicity, drug dosing will be interrupted or modified according to rules described in [Table 2](#), [Table 3](#), and [Table 4](#).

If the toxicity is tolerable to the patient, the initial dose should be maintained. If the toxicity is intolerable to the patient, RAD001 treatment is to be interrupted until recovery to grade ≤ 1 , then reintroduced at the initial dose or a lower dose level, depending on toxicity type and grade (see [Table 3](#)). All interruptions or dose modifications must be recorded on the Dosage Administration Record CRF.

Table 2 RAD001 Dose Level Modification Guidelines

Dose Level	Dose Schedule
0	10 mg daily
1	5 mg daily
2	5 mg every other day

Table 3 provides the procedure to be followed for dose modification and re-initiation of RAD001 in the event of toxicities suspected to be related to the study drug.

Table 3 Criteria for Dose Modification in Case of Suspected RAD001 Toxicity

Toxicity	Actions
Non-hematological toxicity	
Grade 1	No dose modification.
Grade 2 (except pneumonitis):	If the toxicity is tolerable to the patient, maintain the same dose. If toxicity is intolerable to the patient, interrupt RAD001 until recovery to grade ≤ 1 , then re-introduce RAD001 at the same dose. If the event returns to grade 2, interrupt RAD001 until recovery to grade ≤ 1 , then re-introduce at the lower dose level.
Grade 3 (except hyperlipidemia):	Interrupt RAD001 until recovery to grade ≤ 1 , then re-introduce at the lower dose level. For pneumonitis, consider the use of a short course of corticosteroids.
Grade 3 hyperlipidemia (hypercholesterolemia and/or hypertriglyceridemia):	Should be managed using standard medical therapies.
Grade 4:	Discontinue RAD001.
Reactivation of HBV or HCV	Please refer to Tables 6 and 7 .
Hematological toxicity	
Grade 1	No dose modification.
Grade 2 thrombocytopenia (platelets $<75 \times 10^9/L$, $\geq 50 \times 10^9/L$):	Interrupt RAD001 until recovery to grade ≤ 1 (platelets $\geq 75 \times 10^9/L$), then re-introduce RAD001 at the initial dose. If thrombocytopenia returns to grade 2, interrupt RAD001 until recovery to grade ≤ 1 , then re-introduce at the lower dose level.

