Grade 3 thrombocytopenia (platelets $<50 \times 10^9/L$, $\geq 25 \times 10^9/L$):	Interrupt RAD001 until recovery to grade ≤ 1 (platelets $\geq 75 \times 10^9/L$), then resume RAD001 at 1 dose level lower. If grade 3 thrombocytopenia recurs, discontinue RAD001.
Grade 4 thrombocytopenia (platelets $<25 \times 10^9/L$):	Discontinue RAD001.
Grade 3 neutropenia (neutrophils $<1 \times 10^9/L$, $\geq 0.5 \times 10^9/L$):	Interrupt RAD001 until recovery to grade ≤ 1 (neutrophils $\geq 1.5 \times 10^9/L$), then resume RAD001 at initial dose. If absolute neutrophil count (ANC) returns to grade 3, hold RAD001 until recovery to grade 1 (ANC $\geq 0.5 \times 10^9/L$), then resume RAD001 at the lower dose level. Discontinue patient from study therapy for a third episode of grade 3 neutropenia.
Grade 4 neutropenia (neutrophils $<0.5 \times 10^9/L$):	Interrupt RAD001 until recovery to grade ≤ 1 (neutrophils $\geq 1.5 \times 10^9/L$), then resume RAD001 at the lower dose level. If grade 3 or grade 4 neutropenia occurs despite this dose reduction, discontinue RAD001.
Grade 3 febrile neutropenia (not life-threatening):	Interrupt RAD001 until resolution of fever and neutropenia to grade ≤ 1 . Hold further RAD001 until the ANC $\geq 1500/mm^3$ and fever has resolved. Resume RAD001 at the lower dose level. If febrile neutropenia recurs, discontinue RAD001.
Grade 4 febrile neutropenia (life-threatening):	Discontinue RAD001.
Any hematological or non-hematological toxicity	Discontinue RAD001.

requiring interruption for ≥ 3 weeks:

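### Tables 3 and 4 give different restart rules for Grade 3 non-infectious pneumonitis, both are said to apply, and the protocol does not say which governs

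*Protocol*

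**What the plan says.** **Table 3 (Protocol 6.1.3).** The Grade 3 non-hematological row carves out only hyperlipidemia. It tells the investigator to interrupt until grade 1 or less, "then re-introduce at the lower dose level. For pneumonitis, consider the use of a short course of corticosteroids". Pneumonitis is therefore named in the row. It is excluded only one row higher, under "Grade 2 (except pneumonitis". The sole time limit in the table is its last row: "Any hematological or non-hematological toxicity" that needs an interruption of 3 weeks or more leads to discontinuation.

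**Table 4 (Protocol 6.1.4.3).** The Grade 3 row also holds treatment until grade 1 or less, and then says: "May restart protocol treatment within 2 weeks at a reduced dose". The reduction is by one level, and the same sentence makes the restart conditional on evidence of clinical benefit. Corticosteroids are to be prescribed once an infective origin has been excluded.

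**Which table applies.** Section 6.1.4.3 begins its pointer with "Dose modification instructions and Management of non-infectious pneumonitis suspected to be associated with RAD001" and refers the reader to Table 3 and Table 4. Section 6.1.3 refers to Tables 2, 3 and 4, and SAP 3.2 repeats that list. None of the three ranks the tables.

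**General time limits.** Section 6.1.4 says "If a patient requires a dose delay of >21 days from the intended day of the next scheduled dose", the patient must come off study. Section 6.6.3.1 repeats this, and 6.6.5 uses the same threshold of more than 21 days for interruptions due to suspected drug-related toxicity.

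**The concern.** An investigator whose patient recovers from Grade 3 pneumonitis must decide whether RAD001 restarts. Table 3 instructs re-introduction. Table 4 permits it, under two extra conditions. If the patient fails one of those conditions, following one table breaches the other. Protocol section 12 states that no authorized deviations exist, so either choice could be recorded as a deviation.

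The decision also determines data the SAP reports: treatment-emergent events leading to permanent discontinuation (SAP 8.1), reasons for stopping treatment (SAP 7.3) and treatment duration (SAP 8.6). The incidence of pneumonitis has its own planned summary in Protocol 10.5.2. With 25 sites in 11 countries and no data monitoring committee, sites could resolve the ambiguity differently without any central correction. For a single-arm study whose secondary objectives include describing the safety profile, part of the discontinuation pattern would then reflect which table a site happened to read.

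**Working it through.** The plan states no figure here, so there is none to reproduce. The check sets the two Grade 3 rules side by side and then applies each to the same patient.

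| Element | Table 3 | Table 4 |
|---|---|---|
| Hold until | grade 1 or less | grade 1 or less |
| Dose at restart | lower level | one level lower |
| Force of the rule | instruction to re-introduce | permission to restart |
| Clinical-benefit condition | none | required |
| Time limit | general row, 3 weeks or more | 2 weeks, start not defined |
| Corticosteroids | consider a short course | prescribe once infection is excluded |

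The tables agree on the first two rows. The restart decision turns on the clinical-benefit condition and the time limit.

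**Rules as conditions.** Let d be the number of whole days from the start of the hold to recovery, and assume restart on the day of recovery, so that d is also the length of the interruption.

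- Table 3: restart if d < 21.
- Table 4, 2 weeks counted from the start of the hold: restart if d ≤ 14 and there is evidence of clinical benefit.
- Table 4, 2 weeks counted from recovery: restart if d < 21 and there is evidence of clinical benefit. The 3-week limit from Table 3 is kept here because it covers any toxicity.

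**Result for d = 1 to 28.**

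| Evidence of clinical benefit | 2 weeks from start of hold | 2 weeks from recovery |
|---|---|---|
| No | tables disagree on days 1–20 | tables disagree on days 1–20 |
| Yes | tables disagree on days 15–20 | no disagreement |

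From day 21 neither table allows a restart, so there is no conflict between them at that point.

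**The 21-day boundary.** Put d = 21 into the general limits. Table 3 stops the drug at 3 weeks or more: 21 ≥ 21 is true, so discontinue. Sections 6.1.4, 6.6.3.1 and 6.6.5 act only above 21 days: 21 > 21 is false, so they do not require discontinuation. This mismatch concerns a single day, but it applies to every suspected drug-related toxicity, not only pneumonitis.

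**Is the no-benefit case realistic?** The dose-modification sections do not define clinical benefit. The first on-treatment tumor assessment is at 8 weeks (Protocol section 4), so a patient with Grade 3 pneumonitis before then may have no response assessment on which to judge it.

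**The case against.** The best defence is that the two tables can be read together. Table 3 is the general toxicity table and Table 4 is specific to pneumonitis. They agree on the hold, the recovery grade and the dose reduction. A site told to use both could treat Table 4's conditions as additions to Table 3, or could let the specific table prevail. Table 3 is merely silent on clinical benefit.

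Both readings are reasonable, but the text settles neither. Table 3 removes pneumonitis from its Grade 2 row and then names it in its Grade 3 row, so a reader cannot take Grade 3 pneumonitis to have been handed over to Table 4. Its wording is also an instruction to re-introduce, not silence on whether to do so.

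The defence does stand against several stronger readings that a reader might infer:

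- **A fixed conflict on days 15 to 21.** This presumes that the 2 weeks start with the hold. Table 4 mentions the window directly after recovery, so counting from recovery is equally open, and then patients with clinical benefit face no conflict. Even when counting from the hold, the range ends at day 20, because Table 3 itself stops the drug at 3 weeks.
- **Contradictory corticosteroid instructions.** The wording differs, but a site can consider steroids, exclude infection and then prescribe. Section 6.1.4.3, which leaves treatment to medical indication, fits that sequence.
- **Pneumonitis as the trial's main safety concern.** The documents do not say this. The synopsis describes it as commonly low-grade and reversible.
- **Damage to the primary endpoint.** Stopping the drug is not a PFS event (Protocol 10.4.1), and tumor assessments continue after discontinuation until new anticancer therapy (6.6.6.1). Any effect on PFS would be indirect.

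**Conclusion.** The protocol contradicts itself on restart after Grade 3 non-infectious pneumonitis. The firm part is the clinical-benefit condition: without such evidence, Table 3 and Table 4 give opposite decisions for any recovery before 3 weeks (days 1 to 20), however the 2 weeks are counted. The time-limit part is conditional: with clinical benefit, the conflict covers days 15 to 20 on one reading and vanishes on the other, and the defect there is that the starting point is undefined. The treatment of an interruption of exactly 21 days is a separate, smaller inconsistency.

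These day ranges assume restart on the day of recovery and that Table 3's 3-week limit also applies to pneumonitis. The documents give no expected frequency of Grade 3 pneumonitis, so the effect on discontinuation counts cannot be sized. The point rests on two written rules that cannot both be followed for the same patient, and it merits correction on that ground. It takes no position on which rule is clinically right.

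**What to change.** Amend the protocol wording so that:

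1. the Grade 3 pneumonitis entries of Tables 3 and 4 agree on whether restart is instructed or permitted, on what conditions and within what time;
2. the day from which the 2-week window is counted is stated and, if a clinical-benefit condition is kept, how it is judged before the first tumor assessment;
3. 6.1.3 states which table governs pneumonitis, and 6.1.4.3 points to the same one;
4. the last row of Table 3 and the limits in 6.1.4, 6.6.3.1 and 6.6.5 treat an interruption of exactly 21 days alike.

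The corticosteroid wording can be aligned in the same pass. The clinical team decides the content of each rule. SAP 3.2 needs a change only if its table references change. The cost is one safety-related protocol amendment with the usual approvals and a notice to sites. Sample size, endpoints and analysis methods are unaffected.

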6.1.4.4 Management of hepatitis reactivation

Monitoring and Prophylactic Treatment for Hepatitis B Reactivation

[Table 5](#) provides details of monitoring and prophylactic therapy according to the screening results of viral load and serologic markers testing.

Test	Result	Result	Result	Result	Result
HBV-DNA	+	+ or -	-	-	-
HBsAg	+ or -	+	-	-	-
HBsAb	+ or -	+ or -	+ and no prior HBV vaccination	+ or -	or + with prior HBV vaccination

HBcAb	+ or -	+ or -	+ or -	+	-
Recommendation	Prophylactic antiviral treatment should be started 1-2 weeks prior to first dose of study drug. Monitor HBV-DNA every 6 weeks		No prophylaxis Monitor HBV-DNA every 3 weeks		No specific action

Table 5 Action to be taken based on Screening Hepatitis B Results

Antiviral prophylaxis therapy should continue for at least 4 weeks after last dose of study drug. For HBV reactivation definition and management guidelines, see [Table 6](#).

Table 6 Guidelines for the management of Hepatitis B reactivation

HBV reactivation (with or without clinical signs and symptoms)*	

For patients with baseline results: Positive HBV-DNA OR positive HBsAg
 
-----
 
reactivation is defined as: [Increase of 1 log in HBV-DNA relative to baseline HBV-DNA value OR new appearance of measurable HBV-DNA] AND ALT elevation x 5 ULN
	
Treat: Start a second antiviral AND Interrupt study drug administration until resolution:
 
 • ≤ grade 1 ALT (or baseline ALT, if > grade 1) and • ≤ baseline HBV-DNA levels 
If resolution occurs within ≤ 28 days, study drug should be re-started at one dose lower, if available (see Table 6-1 for dose levels available). If the patient is already receiving the lowest dose of study drug according to the protocol, the patient should restart at the same dose after resolution. Both antiviral therapies should continue at least 4 weeks after last dose of study drug.
 
If resolution occurs > 28 days, patients should discontinue study drug but continue both antiviral therapies at least 4 weeks after last dose of study drug.


For patients with baseline results: Negative HBV-DNA and HBsAg
 
AND [Positive HBsAb (with no prior history of vaccination against HBV), OR positive HBcAb]
 
-----
 
reactivation is defined as: New appearance of measurable HBV-DNA
	
Treat : Start first antiviral medication AND Interrupt study drug administration until resolution:
 
 • ≤ baseline HBV-DNA levels 
If resolution occurs within ≤ 28 days, study drug should be re-started at one dose lower, if available (see Table 6-1 for dose levels available). If the patient is already receiving the lowest dose of study drug according to the protocol, the patient should restart at the same dose after resolution. Antiviral therapy should continue at least 4 weeks after last dose of study drug.
 
If resolution occurs > 28 days Patients should discontinue study drug but continue antiviral therapy at least 4 weeks after last dose of study drug.

* All reactivations of HBV are to be recorded as grade 3 (CTCAE Version 3.0 – Metabolic Laboratory/Other: Viral Reactivation), unless considered life threatening by the investigator, in which case they should be recorded as grade 4. Date of viral reactivation is the date on which DNA (and ALT) criteria were met (e.g., for a patient who was HBV-DNA positive on 01-JAN-10 and whose ALT reached ≥ 5 × ULN on 01-APR-10, the date of viral reactivation is 01-APR-10).
	

Monitoring for Hepatitis C Reactivation

The following two categories of patients should be monitored every 6 weeks for HCV reactivation:

- Patients with detectable HCV RNA-PCR test at baseline
- Patients known to have a history of HCV infection, despite a negative viral load test at baseline (including those that were treated and are considered „cured“)

For definitions of HBV or HCV reactivation and actions to be taken in the event of reactivation, please refer to [Table 7](#).

Table 6 Guidelines for the management of Hepatitis C reactivation

HCV reactivation*	
For patients with baseline results: Detectable HCV-RNA reactivation is defined as: ALT elevation x 5 ULN	Discontinue study drug
For patients with baseline results: Knowledge of past hepatitis C infection with no detectable HCV-RNA reactivation is defined as: New appearance of detectable HCV-RNA	Discontinue study drug
* All reactivations of HCV are to be recorded as grade 3 (CTCAE Version 3.0 – Metabolic Laboratory /Other: Viral Reactivation), unless considered life threatening by the investigator; in which case they should be recorded as grade 4.	

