Dose, regimen, treatment cycle	
Patients will be instructed to take two 5 mg RAD001 tablets (one tablet after another) orally, with a glass of water at the same time each day in a fasting state or with a light fat-free meal.
 
RAD001 will be taken daily from Visit 2 (Day 1) until disease progression, unacceptable toxicity, or death or discontinuation from the study for any other reason.

Investigational drug	RAD001 (everolimus)
Protocol no.	CRAD001LIC01
Study phase	Phase 2
Study title	An open-label, multi-center phase 2 study to evaluate everolimus as monotherapy treatment for patients with metastatic recurrent and/or unresectable renal cell carcinoma (EVERMORE)
	Each treatment cycle is 28 days.
Supply, preparation, and administration	RAD001 will be provided by Novartis. RAD001 is formulated as tablets of 5 mg strength for oral administration. The starting dose for Cycle 1 is 10 mg/day. Tablets should be opened only at the time of administration, as the drug is both hygroscopic and light sensitive. Patients will be supplied with enough tablets for a complete 28-day cycle. Tablets should be stored in a secure, dry, light-proof medicine cabinet.
Visit schedule and assessments	Patients will present to the clinic on Day 1 and Day 15 of treatment Cycles 1, 2, and 3 and Day 1 of each subsequent treatment cycle for assessments. Please see Section 7 and Table 9 for details of assessments.
Efficacy assessment(s)	
Tumor response, SD, and progression will be assessed using the RECIST criteria. A computerized tomography (CT) scan or magnetic resonance image (MRI) of the chest/abdomen and pelvis will be obtained at screening (≤ 35 days) prior to the first dose of RAD001. Tumor response will be assessed at 8 weeks (± 1 week), and every 12 weeks (± 1 week) thereafter, until determination of disease progression (by the local radiologist) and at the end of the study. The same imaging modality used at screening must be used for all subsequent follow-up assessments.
 
Ultrasound scans cannot be used to measure tumor lesions.

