 - ^u After discontinuation of the study drug, the investigator or his/her designee will collect information on the initiation of new anticancer therapies given after the last dose of study drug.
 - ^v All patients will be screened for HBV-DNA, HBV serologic markers and HCV RNA-PCR. It is highly recommended that patients positive for HBV-DNA or HBsAg receive prophylactic antivirals for 1-2 weeks prior to receiving study drug. The antiviral treatment should continue throughout the entire study period and for at least 4 weeks after the last dose of study drug. Monitoring for HBV reactivation, according to [Table 6-5](#), will only require the measurement of HBV-DNA from Visit 2 onwards. Patients who are HBV-DNA / HBsAg positive at screening will be monitored every cycle. Patients who are HBV-DNA and HBsAg negative at screening (and not receiving prophylaxis) but HBsAb or HBcAb positive will be monitored every cycle. Follow-up testing for HCV RNA-PCR will be performed every cycle only if the patient has a history of HCV or is positive at baseline, or both. If there is no history of HCV and HCV RNA-PCR test is negative at baseline, no follow-up testing is required.

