7.1 Visit Windows

For Cycles 1, 2, and 3, visits will be on the 1st and 15th day (± 5 days) of each 28-day cycle. For each subsequent cycle, patients will return to the site on the 1st day (± 5 days) of each 28-day cycle.

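### Protocol Table 5 and the Table 9 hepatitis footnote set conflicting HBV-DNA monitoring rules, and the group without antiviral prophylaxis is tested less often under Table 9

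*Protocol*

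**What the plan says.** Section 6.1.4.4, Table 5, sorts patients by their hepatitis B screening results into three actions.

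- **On prophylaxis** (HBV-DNA or HBsAg positive): antiviral prophylaxis, and "Monitor HBV-DNA every 6 weeks".
- **Without prophylaxis** (both negative, and either HBcAb positive or HBsAb positive without vaccination): "No prophylaxis Monitor HBV-DNA every 3 weeks".
- **Vaccinated** (both negative, HBcAb negative, HBsAb "or + with prior HBV vaccination"): "No specific action".

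The hepatitis footnote to Table 9 (Section 7) sends the reader to a Table 6-5 and then states its own intervals. For the first group: "Patients who are HBV-DNA / HBsAg positive at screening will be monitored every cycle". For the second: "Patients who are HBV-DNA and HBsAg negative at screening (and not receiving prophylaxis) but HBsAb or HBcAb positive will be monitored every cycle". It has no exception for vaccination. The synopsis (dose, regimen, treatment cycle) says "Each treatment cycle is 28 days". Section 7.1 sets the visit window; after Cycle 3, "patients will return to the site on the 1st day (± 5 days) of each 28-day cycle".

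No table in this protocol is numbered 6-5, although the synopsis (special safety assessments) also refers to it for hepatitis B monitoring.

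**The concern.** A site cannot follow both pages. Some differences only add blood tests, but in the group without prophylaxis Table 9 gives the longer interval. For that group, Table 6 (hepatitis B) defines reactivation as newly measurable HBV-DNA, with no ALT criterion. That single result leads to study drug interruption and a first antiviral.

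The note under Table 6 dates a reactivation by the day its criteria were met and records it as grade 3, or grade 4 if life-threatening. The testing schedule therefore affects when drug is interrupted and what date enters the safety record. Two sites with identical patients could record different dates because they worked from different pages.

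**Working it through.** **Inputs.** Table 5: 3 weeks = 21 days without prophylaxis, 6 weeks = 42 days with it, no testing for the vaccinated HBcAb-negative group. Table 9 footnote: every cycle = 28 days. Window: ±5 days (Section 7.1).

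**Tests after Day 1** = follow-up days ÷ interval. Over 24 weeks = 168 days:

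| Group | Table 5 | Table 9 footnote |
|---|---|---|
| Without prophylaxis | 168/21 = 8 | 168/28 = 6 |
| On prophylaxis | 168/42 = 4 | 168/28 = 6 |
| HBsAb+ by vaccination, HBcAb− | 0 | 168/28 = 6 |

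Without prophylaxis, the footnote gives (8 − 6)/8 = 25% fewer tests. The Table 9 grid, as it reads in the text available, also marks Cycle 3 Day 15 (Day 71). If that mark is real, the Table 9 count becomes 7; the other gaps remain 28 days.

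**Longest gap.** The nominal gap is 21 against 28 days. With one Day 1 visit early and the next late, Table 9 allows 28 + 5 + 5 = 38 days. Table 5 states no window; if the same one applied, its limit would be 21 + 5 + 5 = 31 days.

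**Detection delay, group without prophylaxis.** Assume that onset is equally likely on any day, that HBV-DNA then persists, and that tests fall on their nominal days. Mean delay is half the interval: 21/2 = 10.5 days (Table 5) and 28/2 = 14 days (Table 9), a difference of 3.5 days.

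The delay is not uniformly longer. Take one 84-day period, with tests at 21, 42, 63 and 84 days after Day 1 (Table 5) and at 28, 56 and 84 (Table 9):

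- Table 9 detects later for onset in 0–21, 28–42 and 56–63: 21 + 14 + 7 = 42 days of onset.
- Table 9 detects earlier for onset in 21–28 and 42–56: 7 + 14 = 21 days.
- Both detect on the same day for onset in 63–84: 21 days.

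**Can the visits deliver a 3-week interval?** Visits fall on Days 1, 15, 29, 43, 57, 71 and 85, then every 28 days (113, 141, 169). Three-weekly tests fall on Days 22, 43, 64, 85, 106, 127, 148 and 169.

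- Days 43, 85 and 169 coincide with visits.
- Day 22 lies between the windows 10–20 and 24–34.
- Day 64 lies between 52–62 and 66–76.
- Days 106, 127 and 148 lie outside the windows 80–90, 108–118, 136–146 and 164–174.

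Thus 3 of 8 tests can be done at scheduled visits and 5 cannot.

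**The case against.** The strongest reply is that the footnote defers to the hepatitis table and is only shorthand for it. On vaccination this is arguable: Table 6 carries the same vaccination exception as Table 5, so the footnote might be meant to import it. On the interval it fails. The footnote states its own frequency for each group, and the table number it cites does not exist here.

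Table 5 also labels its action row a recommendation, and Section 4 calls Section 6.1.4.4 management guidelines, so it would be too strong to say that Table 5 imposes an absolute requirement. Against that, its title speaks of action to be taken, and the synopsis says patients will be monitored according to the hepatitis table.

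A reader might infer more than the documents support:

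- That Table 9 under-tests HBV-exposed patients generally. It does so in one group of three.
- That Table 5 exempts every vaccinated patient. The exemption needs a negative HBcAb; a vaccinated HBcAb-positive patient falls in the 3-week column.
- That Table 9 always finds reactivation later. This holds only on average.
- That the number of reactivations would change. Persistent HBV-DNA is found on either schedule. The count changes only if viraemia clears between tests or testing stops first, and the documents give no basis for assuming that.
- That a 3-week test never meets a visit. Some do.

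It also stands that HBV-DNA enters no efficacy endpoint, that the SAP plans no HBV-DNA output (Sections 8.3 and 11), and that the number of affected patients is not given.

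**Conclusion.** The contradiction is real and lies in current protocol text. For patients without prophylaxis it amounts to 8 against 6 tests in 24 weeks (7 if the Cycle 3 Day 15 mark counts) and a nominal gap of 21 against 28 days, up to 38 with the window. The mean detection delay differs by about 3.5 days, assuming uniform onset and persistent viraemia and leaving out the possible extra test. For patients on prophylaxis and, on a literal reading, vaccinated HBcAb-negative patients, Table 9 means more testing, not less.

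The consequence is limited to the timing of detection and of the actions that follow it, and to the recorded reactivation date. The primary PFS analysis is not directly at stake. The point should be fixed because the less-tested group has no antiviral cover and HBV-DNA is its only reactivation criterion.

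**What to change.** Reconcile Table 5 and the Table 9 hepatitis footnote so that both give the same HBV-DNA interval for each risk group and the same rule for HBsAb-positive, HBcAb-negative vaccinated patients. In the same edit:

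- replace the Table 6-5 reference in the footnote and the synopsis with the correct table number;
- confirm whether the Cycle 3 Day 15 mark in the grid is intended;
- provide visits, or explicit laboratory-only draws with a window, that can deliver the chosen interval;
- settle the parallel HCV RNA conflict, which is every 6 weeks in the synopsis and Section 6.1.4.4 but every cycle in this footnote.

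Which interval and which vaccination rule are right is for the sponsor's clinical team. The SAP is dated September 2017, after the planned last visit of January 2012. If the protocol can no longer be amended, the study report should say which schedule sites followed and which one was used to judge deviations.

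The cost is amendment wording and, depending on the choice, a few more or fewer blood tests or visits in HBV-exposed patients.
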